9.4. Safety Follow-up Visit

Patients who complete the active treatment phase or who discontinue due to unacceptable toxicity will be followed-up for 28 days after the last dose of neratinib to collect SAEs.

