13.2. Reporting Adverse Events

For serious and non-serious AEs, the reporting period to the Sponsor (or its designated representative) begins from the time that the patient provides informed consent, which is obtained prior to the patient's participation in the study, i.e., prior to undergoing any study-related procedure and/or receiving investigational product, through 28 calendar days after the last administration of the investigational product.

For all AEs with causal relationship to the investigational product, follow-up by the Investigator may be required until the event or its sequelae resolve or stabilize at the level acceptable to the Investigator, and the Sponsor concurs with that assessment.

If a patient begins a new anticancer therapy, the AE reporting period for non-serious AEs ends at the time the new treatment is started. Death must be reported if it occurs during the SAE reporting period after the last dose of investigational product, irrespective of any intervening treatment.

The Sponsor will evaluate any safety information that is spontaneously reported by an Investigator beyond the time frame specified in the protocol.

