17. APPENDICES

APPENDIX 1. SCHEDULE OF PROCEDURES

Table A1.1. Schedule of Study Procedures – Neratinib Monotherapy in the Extended Adjuvant Setting

Study Procedures	Screening ^a Days -28 to -1	Active Treatment ^b Cycle / Day (C/D)				Safety Follow-up Visit 28 Days After Last Dose
		C1/D1 (28-day cycle)	Colonoscopy 2	Post-second colonoscopy Visit 1-2-3	EOT Visit	
Study visit window in Days	0	-3 ^b	+/-3	Every 3 months ±10	±5	+5
Informed consent ^c	X					
Medical/Cancer history/Demography ^d	X					
ERBB2 status documentation ^e	X					
ECOG performance status	X					
Serum or urine β-hCG ^f	X	X				
Physical examination ^g	X	X	X	X	X	
Vital signs ^h	X	X				X
CBC plus differential ⁱ	X	X				
Serum chemistry ^j	X	X				
Liver function tests ^k	X	X		X		
INR	X					
ESR and CRP ^l		X	X			
MUGA or ECHO ^m	X					
ECG (12-lead)	X					
Colonoscopy ⁿ		X	X			
Fecal calprotectin and fecal elastase		X	X			
Concomitant medications or treatments ^o	X	X	X	X		
Neratinib administration ^p		Continuous once-daily dosing (pill count at each visit)				
Loperamide administration ^q		Loperamide dosing during C1	As needed			
Adverse events ^r		X	X-----X		X	

Abbreviations: β-hCG=beta-human chorionic gonadotropin; ALP=alkaline phosphatase; ALT=alanine aminotransferase; AST=aspartate aminotransferase; BUN=blood urea nitrogen; C=cycle; CBC=complete blood count; CRP = C-reactive protein; D=day; ECG= electrocardiogram; ECHO=echocardiogram; ECOG=Eastern Collaborative Oncology Group; eCRF=electronic case report form; EOT = end of treatment; ESR = erythrocyte sedimentation rate; FISH =

fluorescence in situ hybridization ; Hb=hemoglobin; Hct=hematocrit; IHC=immunohistochemistry; INR = International Normalized Ratio; LFT=liver function test; LDH=lactate dehydrogenase; MUGA=multiple-gated acquisition scan; NP=nurse practitioner; PA=physician's assistant; RBC=red blood cell; SAE=serious adverse event; TEAE=treatment-emergent adverse event; WBC=white blood cell.

- ^a Screening procedures and enrollment may occur on one day, however, enrollment must not be done before all screening procedures have been completed and results confirming eligibility have been reviewed.

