^r From the signing of the informed consent form through 28 days of neratinib monotherapy following the second study colonoscopy procedure in patients with stage 1 to 3c breast cancer treated in the extended adjuvant setting, and in Cycle 2 in patients with mBC, TEAEs and SAEs will be monitored continuously and recorded in the eCRF. Patients must use the diary to document any episodes of diarrhea for the first cycle (28 days) of the study.

^r After the completion of Cycle 2 through 28 calendar days after the last administration of neratinib, only SAE data will be collected. Should an Investigator be made aware of any SAEs occurring any time after the reporting period that may be causally related to administration of neratinib, it should be promptly reported. All SAEs must be reported within 24 hours of awareness of the event using the SAE Report Form.

Table A1.2. Schedule of Study Procedures – Neratinib In Combination with Capecitabine in Metastatic Breast Cancer

Study Procedures	Screening ^b Days -28 to -1	Active Treatment ^a Cycle / Day (C/D)				Treatment Discontinuation 0-3 Days After Last Dose	Safety Follow-up Contact 28 Days After Last Dose
		C1/D1 (28-day)	C2/D1 (21-day)	Colonoscopy 2	C3+ (21-day) ^{q,r}		
Study visit window in Days	0	-3 ^b	±5		±5		±5
Informed consent ^c	X						
Medical/Cancer history/Demography ^d	X						
ERBB2 status documentation ^e	X						
ECOG performance status	X						
Serum or urine β-hCG ^f	X	X					
Physical examination	X	X ^g	X ^g		X ^g	X ^g	
Vital signs ^h	X	X	X		X	X	
CBC plus differential ⁱ	X	X			X	X	
Serum chemistry ^j	X	X			X	X	
Liver function tests ^k	X	X	X		X	X	
INR	X						
ESR and CRP ^l		X		X			
MUGA or ECHO ^m	X				X		
ECG (12-lead) ⁿ	X				X	X	
Colonoscopy ^o		X		X			
Fecal calprotein and fecal elastase		X		X			
Concomitant medications or treatments ^p	X	X	X	X	X		
Neratinib administration ^q		Continuous once-daily dosing (pill count at each visit)					
Capecitabine ^r			X		X		

Study Procedures	Screening ^b Days -28 to -1	Active Treatment ^a Cycle / Day (C/D)				Treatment Discontinuation 0-3 Days After Last Dose	Safety Follow-up Contact 28 Days After Last Dose
		C1/D1 (28-day)	C2/D1 (21-day)	Colonoscopy 2	C3+ (21-day) ^{q,r}		
Study visit window in Days	0	-3 ^b	±5		±5		±5
Loperamide administration ^q		Loperamide dosing during C1		As needed			
Adverse events ^{s,t}		X ^s	X ^t				X

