- ^q Loperamide is to be administered as per instructions in [Section 6.2](#). Patients are asked to document administration of neratinib and loperamide in a diary on a daily basis during the first cycle (28 days) of the study, and to return this diary to the site at appropriate visit. Individual patient dosing compliance should be reviewed by study site staff. Investigators must ensure that patients have loperamide on hand when starting to take neratinib. Neratinib will be dispensed directly by the study sites on or before Cycle 1/Day 1 and during subsequent visits as needed. Loperamide is the recommended standard therapy to treat diarrhea in this study. If alternative antidiarrheal medication is used, the reason must be documented in the source documents. Acceptable reasons are non-tolerance of loperamide or lack of efficacy.
- ^r Capecitabine therapy will begin following the completion of the second study colonoscopy procedure and will be administered on Day 1-14 of each cycle. **Note: capecitabine cannot be administered until after the second study colonoscopy procedure is completed.**
- ^s From the signing of the informed consent form through the end of Cycle 2 TEAEs and SAEs will be monitored continuously and recorded in the eCRF. Patients must use the diary to document any episodes of diarrhea for the first cycle (28 days) of the study.
- ^t After the completion of Cycle 2 through 28 calendar days after the last administration of neratinib, only SAE data will be collected. Should an Investigator be made aware of any SAEs occurring any time after the reporting period that may be causally related to administration of neratinib, it should be promptly reported. All SAEs must be reported within 24 hours of awareness of the event using the SAE Report Form.

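### Table A1.2 lets the mBC safety follow-up contact fall up to 5 days before the 28-day SAE and on-study death period ends; Table A1.1 does not allow this for stage 1 to 3c patients

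*Protocol*

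**What the plan says.** Protocol Appendix 1 has two schedules. For mBC patients, Table A1.2 ends with the "Safety Follow-up Contact 28 Days After Last Dose". Its window row reads "Study visit window in Days 0 -3 ^b ±5 ±5 ±5", and the last entry belongs to the follow-up column. For stage 1 to 3c patients, Table A1.1 ends with the "Safety Follow-up Visit 28 Days After Last Dose", and its window row closes with "Every 3 months ±10 ±5 +5", so the follow-up entry is +5.

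The collection period is the same length in both groups. Table A1.2 footnote t states: "After the completion of Cycle 2 through 28 calendar days after the last administration of neratinib, only SAE data will be collected". Protocol Section 13.2 runs the AE and SAE reporting period "through 28 calendar days after the last administration of the investigational product". Section 9.4 says that patients who complete active treatment or stop for unacceptable toxicity "will be followed-up for 28 days after the last dose of neratinib to collect SAEs". Section 9.6 extends the 28-day follow-up to all patients as the condition for ending the study. SAP Section 6.9.4 lists on-study deaths as a yes/no variable over the 28 days after the last neratinib dose.

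Section 4.1 places the mBC follow-up at 28 days without a window, and no other section overrides either table.

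**The concern.** A visit whose purpose is to close out a 28-day safety period should not be allowed before that period ends. Under Table A1.2 it is. After the treatment discontinuation visit, set at 0 to 3 days after the last dose, the follow-up contact is the only remaining scheduled contact for an mBC patient. If it is held early, nothing planned covers the days up to Day 28.

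Three items depend on those days:

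- **The SAE listing.** After Cycle 2, SAEs are the only adverse event data collected.
- **The SAP's on-study death variable.** A contact on Day 23 shows that the patient was alive on Day 23. It cannot by itself support a 'no' for the full 28 days.
- **The record that follow-up was completed.** Section 9.6 first requires 28 days of follow-up for everyone, then defines end of study as the last patient's last safety follow-up visit or completion of all follow-up and data collection. If the last patient has mBC and is contacted on Day 23, the visit limb is met while the 28-day condition is not. The synopsis also makes the final analysis wait for completed Safety Follow-up Visits, a condition that an early contact could satisfy.

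The documents give no reason for the two groups to have different windows.

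**Working it through.** The plan states no figure for this point, so there is none to reproduce. The check is day arithmetic, counting the last neratinib dose as Day 0.

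**Inputs**

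- Nominal follow-up day: 28 in both groups (Tables A1.1 and A1.2).
- Window: ±5 for mBC (Table A1.2), +5 for stage 1 to 3c (Table A1.1).
- End of SAE collection: Day 28 (Table A1.2 footnote t; Section 13.2).
- End of the on-study death period: Day 28 (SAP Section 6.9.4).

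**Column check.** Table A1.2 has seven columns: screening, C1/D1, C2/D1, second colonoscopy, C3+, treatment discontinuation and safety follow-up. The window entries are 0, -3, ±5, blank, ±5, blank, ±5, so the final ±5 sits under safety follow-up. The row is printed again, with the same values, where the table continues. In Table A1.1 the six entries are 0, -3, +/-3, ±10, ±5 and +5, so +5 sits under safety follow-up and ±5 under EOT.

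**Formulas**

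- Earliest contact = 28 + lower window limit.
- Latest contact = 28 + upper window limit.
- Largest gap = 28 − earliest contact.

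| | Earliest | Latest | Largest gap | Share of 28 days |
|---|---|---|---|---|
| mBC (±5) | 28 − 5 = Day 23 | 28 + 5 = Day 33 | 28 − 23 = 5 days (Days 24 to 28) | 5/28 = 17.9% |
| Stage 1 to 3c (+5) | 28 + 0 = Day 28 | 28 + 5 = Day 33 | 28 − 28 = 0 days | 0% |

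With +5 applied to the mBC contact, its row becomes identical to the stage 1 to 3c row: Day 28 to Day 33, with no gap.

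**The case against.** The strongest reply is that the window governs a contact, not the collection obligation. The reporting period in Section 13.2 runs to Day 28 whenever the contact takes place. Section 13.3 requires every SAE to be reported within 24 hours of discovery or notification, whatever its relationship to treatment. Section 13.2 also requires deaths in the SAE reporting period to be reported irrespective of any intervening treatment. All of this stands.

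It rules out a stronger reading that a reader might infer: that SAEs after an early contact are captured only if they may be drug-related. The causality condition in Section 13.3 and footnote t applies to SAEs after the reporting period, not after the last contact. An SAE on Day 25 is reportable whatever its cause. For the same reason the documents do not support calling Days 24 to 28 unobserved, or calling SAE collection incomplete by design. What can be missing is the scheduled prompt through which the site would learn of an event.

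The second reply is materiality, and it also largely stands. The study plans 3 to 5 patients with no minimum number with mBC. The primary endpoint is the biopsy change after the first 28 days of treatment, which this window does not touch. The SAP's treatment-emergent period for mBC patients ends with Cycle 2, so for anyone treated beyond that only the SAE and death listings are affected. The SAP plans no comparison between the two disease groups, so the difference in windows biases no planned contrast. On the other side, results are presented mainly as listings and narratives, and in so small a study one missed SAE or death would be a visible omission.

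Third, the contrast between tables rests on a single sign, and signs can be lost when a PDF is read. The repeated row in Table A1.2 makes an error there unlikely. If the +5 in Table A1.1 were misread, the contrast would go but the Day 23 result for mBC would not.

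**Conclusion.** The point holds as a minor inconsistency between a visit window and the period that the visit should cover. A compliant mBC contact can precede the end of the SAE and on-study death periods by at most 5 of 28 days (17.9%). For stage 1 to 3c patients the corresponding figure is 0. The loss is of scheduled ascertainment and of documented 28-day follow-up; the duty to report is unaffected. The 17.9% is a worst-case scheduling gap per mBC patient, not an expected loss of data: a contact on or after Day 28 leaves no gap, and an event in the gap is still captured if the site hears of it. The expected number of missed events is small, and the documents give no event rate from which to compute it.

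This rests on reading the two window rows as printed, on counting days from the last neratinib dose, and on there being no further mBC contact in the study manuals, which are not part of these documents.

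**What to change.** In Table A1.2, change the window for the safety follow-up contact from ±5 to +5 so that the contact cannot precede Day 28. This matches Table A1.1 and brings the schedule into line with footnote t, Sections 9.4, 9.6 and 13.2, and SAP Section 6.9.4. Because the window row is printed twice, both copies need the change.

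The cost is one table entry and some scheduling flexibility. The latest permitted day stays at 33, and the permitted span shrinks from 11 days (Days 23 to 33) to 6 days (Days 28 to 33). No treatment, analysis or sample size changes.

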APPENDIX 2. INVESTIGATIONAL PRODUCT DOSE ADJUSTMENT FOR TOXICITY

1. Dose adjustment levels

Recommended dose reductions for the -1 and -2 dose levels of **neratinib** and **capecitabine** are listed in [Table 3](#) in [Section 6.1.1](#) and in [Table 6](#) in [Section 6.3.1](#).

2. Toxicities Requiring Investigational Product Dose Adjustments

General Toxicities:

The guidelines for dose adjustments of **neratinib** and **capecitabine** for general toxicities due to the combination of **neratinib** plus **capecitabine** are shown in [Table A2.1](#).

Table A2.1. General Toxicities Requiring Dose Adjustment of Neratinib

NCI CTCAE v.4.0	Action
Grade 2 adverse reaction	
• 1st appearance	• Hold neratinib and capecitabine until event resolves to Grade ≤ 1 ; then resume neratinib at the starting dose level.
• 2nd appearance	• Hold neratinib and capecitabine until event resolves to Grade ≤ 1 ; then resume neratinib at 160 mg and capecitabine at 1100 mg/m ² (550 mg/m ² BID).
• 3rd appearance	• Hold neratinib and capecitabine until event resolves to Grade ≤ 1 ; then resume neratinib at 120 mg and capecitabine at 750 mg/m ² (375 mg/m ² BID).
• 4th appearance	• Discontinue neratinib and capecitabine permanently.
Grade 3 adverse reaction	
• 1st appearance	• Hold neratinib and capecitabine until event resolves to Grade ≤ 1 ; then resume neratinib at 160 mg and capecitabine at 1100 mg/m ² (550 mg/m ² BID).
• 2nd appearance	• Hold neratinib and capecitabine until event resolves to Grade ≤ 1 ; then resume neratinib at 120 mg and capecitabine at 750 mg/m ² (375 mg/m ² BID).
• 3rd appearance	• Discontinue neratinib and capecitabine permanently.
Grade 4 adverse reaction	
• 1st appearance	• Discontinue neratinib and capecitabine permanently OR if Investigator deems it to be in the patient's best interest to continue, hold neratinib and capecitabine until resolved to Grade ≤ 1 ; then resume neratinib at 120 mg and capecitabine at 750 mg/m ² (375 mg/m ² BID). • If the event occurs again despite one dose reduction, permanently discontinued neratinib .

Abbreviations: BID: twice daily; NCI CTCAE v4.0, National Cancer Institute Common Terminology for Adverse Events Version 4.0.

Gastrointestinal Toxicity:

Guidelines for adjusting doses of **neratinib** and **capecitabine** in the event of gastrointestinal toxicity diarrhea are shown in [Table A2.2](#).

Table A2.2. Gastrointestinal Toxicities Requiring Dose Adjustment of Neratinib and Capecitabine

NCI CTCAE V4.0	Action

 Grade 1 Diarrhea [Increase of <4 stools per day over baseline; mild increase in ostomy output compared to baseline.] OR Grade 2 Diarrhea [Increase of 4-6 stools per day over baseline; moderate increase in ostomy output compared to baseline;] lasting <5 days OR Grade 3 Diarrhea [Increase of ≥ 7 stools per day over baseline; incontinence; hospitalization indicated; severe increase in ostomy output compared to baseline limiting self-care activities of daily living (ADL)] lasting ≤ 2 days 
 Persisting and intolerable Grade 2 Diarrhea lasting ≥ 5 days despite being treated with optimal medical therapy, or associated with fever, dehydration, or Grade 3-4 neutropenia OR Grade 3 Diarrhea lasting > 2 days despite being treated with optimal medical therapy, or associated with fever, dehydration, or Grade 3-4 neutropenia OR Any Grade 4 diarrhea [Life-threatening consequences; urgent intervention indicated] 	
 Adjust anti-diarrheal treatment, as per the guidelines for management of diarrhea at the first onset of diarrhea (refer to Section 6.2 and Section 7.2). Continue neratinib and capecitabine at full dose. Instruct patient to follow dietetic recommendations in the guidelines for management of diarrhea (refer to Section 7.2). Fluid intake of ~ 2L should be maintained to avoid dehydration. Once the event resolved to \leq Grade 1 or baseline, start loperamide 4 mg with each subsequent neratinib administration. 
 Adjust anti-diarrheal treatment, as per the guidelines for management of diarrhea at the first onset of diarrhea (refer to Section 6.2 and Section 7.2). Hold neratinib and capecitabine until recovery to \leq Grade 1 or baseline. Instruct patient to follow dietetic recommendations of the guidelines for management of diarrhea. Fluid intake of ~ 2L should be maintained, intravenously if needed. If recovery occurs: 
 ≤ 1 week after withholding treatment, resume same dose of neratinib and capecitabine. Within 1-4 weeks after withholding treatment, reduce neratinib dose to the next lower dose level and maintain the same dose of capecitabine. If event occurs a 2nd time and the neratinib dose has not already been decreased, reduce neratinib dose to the next lower dose level and maintain the same dose of capecitabine. If neratinib dose has already been reduced, then reduce the dose of capecitabine to 1100 mg/m^2^a (550 mg/m^2 BID) (maintain same dose of neratinib) If subsequent events occur, reduce the dose of neratinib or capecitabine to the next lower dose level in an alternate fashion (i.e., reduce capecitabine to 750 mg/m^2 (375 mg/m^2 BID) if neratinib was previously reduced, or reduce neratinib to 120 mg if capecitabine was previously reduced.. Once the event resolved to \leq Grade 1 or baseline, start loperamide 4 mg with each subsequent neratinib administration.

Abbreviations: BID: twice daily; IV: intravenous; L: liter; NCI CTCAE v4.0: National Cancer Institute Common Terminology Criteria for Adverse Events version 4.0.

^a Since capecitabine is provided as 150 mg or 500 mg tablets, it is recommended that the capecitabine dose reduction(s) is rounded down to the nearest 500 mg or multiple of 150 mg for the BID dose. If the patient's body surface area is >2.0 , the standard of care for the study center can be utilized for capecitabine mg/m^2 dosing.

Pulmonary Toxicity:

Guidelines for adjusting doses of **neratinib** in the event of pulmonary toxicities are shown in [Table A2.3](#). Interstitial lung disease, which can sometimes be fatal, has been reported with other oral tyrosine kinase inhibitors that target EGFR ±HER2 (*ERBB2*), including lapatinib, gefitinib, and erlotinib. Rare cases of pneumonitis (0.6%) and lung infiltration (0.4%) have been reported in patients treated with **neratinib** monotherapy, and considered drug-related. Patients receiving **neratinib** should be monitored for acute onset or worsening of pulmonary symptoms such as dyspnea, cough, and fever and treated appropriately.

Table A2.3. Pulmonary Toxicities Requiring Dose Adjustment of Neratinib

NCI CTCAE V4.0	Action

Grade 2 Pneumonitis/Interstitial Lung Disease [Symptomatic; medical intervention indicated; limiting instrumental ADL]	
Hold neratinib until recovery to \leq Grade 1 or baseline.Reduce neratinib to 160 mg or discontinue neratinib as per Investigator's best medical judgment.

Grade \geq3 Pneumonitis/Interstitial Lung Disease [Severe symptoms; limiting self-care ADL; oxygen indicated]	
Discontinue neratinib permanently.

Abbreviations: NCI CTCAE v4.0: National Cancer Institute Common Terminology Criteria for Adverse Events version 4.0.

Liver Toxicity:

Guidelines for adjustment of **neratinib** and **capecitabine** in the event of liver toxicity are shown in [Table A2.4](#).

Abnormal values in ALT concurrent with abnormal elevations in total bilirubin that meet the criteria outlined below in the absence of other causes of liver injury are considered potential cases of drug-induced liver injury (potential Hy's Law cases) and should always be considered important medical events.

Patients who experience \geq Grade 3 diarrhea requiring IV fluid treatment or any signs or symptoms of hepatotoxicity such as worsening of fatigue, nausea, vomiting, right upper quadrant pain or tenderness, fever, rash or eosinophilia should be evaluated for changes in liver function tests. Fractionated bilirubin and prothrombin time must also be collected during hepatotoxicity evaluation.

Table A2.4. Liver Function Test Abnormalities Requiring Dose Adjustment of Neratinib

NCI CTCAE V4.0	Action
Grade 3 ALT (>5 – 20x ULN) OR Grade 3 bilirubin (>3-10x ULN)	
 Hold neratinib and capecitabine until recovery to \leq Grade 1 for patients with ALT \leq Grade 1 at baseline OR \leq Grade 2 for patients with Grade 2 ALT at baseline. Evaluate alternative causes. For patients with ALT $<$ Grade 1 at baseline: Resume neratinib at the next lower dose level (160 mg) and capecitabine at the next lower dose level (1100 mg/m² [550 mg/m² BID])^a if recovery to \leq Grade 1 occurs within 4 weeks. If Grade 3 ALT or bilirubin occurs again despite one dose reduction, permanently discontinue neratinib and capecitabine.
Grade 4 ALT (>20x ULN) OR Grade 4 Bilirubin (>10x ULN)	
 Permanently discontinue neratinib and capecitabine. Evaluate alternative causes.
ALT >3x ULN AND Total bilirubin >2x ULN AND Alkaline phosphatase <2x ULN (potential Hy's law indicators of drug-induced liver damage)	
 Hold neratinib and capecitabine. The patient should return to the investigational site and be evaluated as soon as possible, preferably within 48 hours from awareness of the abnormal results. This evaluation should include laboratory tests, detailed history and physical assessment and for oncology studies, the possibility of hepatic neoplasm (primary or secondary) should be considered. In addition to repeating AST and ALT, laboratory tests should include albumin, total bilirubin, direct bilirubin, PT and alkaline phosphatase. A detailed history, including relevant information, such as review of ethanol, concomitant medications, recreational drug and supplement consumption, family history, sexual history, travel history, history of contact with a jaundiced patient, surgery, blood transfusion, history of liver or allergic disease, and work exposure, should be collected. Further testing for acute hepatitis A, B, or C infection and liver imaging (eg, biliary tract) may be warranted. All cases confirmed on repeat testing as meeting the criteria mentioned above (i.e., ALT $>$ 3 x ULN associated with bilirubin $>$ 2 x ULN and alkaline phosphatase $<$ 2 x ULN), with no other cause for liver function test abnormalities identified at the time should be considered potential Hy's Law cases, irrespective of availability of all the results of the investigations performed to determine etiology of the abnormal liver function tests. Contact the Sponsor immediately to discuss next steps, including evaluation of alternative causes, and management of investigational product. These events must be reported as SAEs.

Abbreviations; ALT=alanine aminotransferase; AST: aspartate aminotransferase; BID: twice daily; PT: prothrombin time; SAE: serious adverse event; ULN: upper limit of normal.

NOTE: During evaluation of hepatotoxicity, bilirubin must be fractionated, prothrombin time must be measured, and liver imaging should be considered.

^a Since capecitabine is provided as 150 mg or 500 mg tablets, it is recommended that the capecitabine dose reduction(s) is rounded down to the nearest 500 mg or multiple of 150 mg for the BID dose. If the patient's body surface area is >2.0, the standard of care for the study center can be utilized for capecitabine mg/m² dosing.

Left Ventricular Ejection Fraction Toxicity

Guidelines for dose adjustments of neratinib in the event of abnormalities in LVEF are shown in **Table A2.5**. LVEF assessments will be performed according to the Schedule of Procedures ([Appendix 1](#)). It is strongly recommended to use the same method of cardiac evaluation (ECHO or MUGA) at each time point for each patient.

Table A2.5: Left Ventricular Ejection Fraction (LVEF) Results Requiring Dose Adjustments of Neratinib

EVENT ON DAY OF SCHEDULED TREATMENT	Action
Asymptomatic absolute decline of LVEF $\geq 15\%$ from baseline OR absolute decline of LVEF $\geq 10\%$ ad below the lower limit of normal of 50%	
A) If LVEF is below 40%: hold neratinib and seek cardiology input OR continue neratinib with great caution.
 
Initiate monthly monitoring of LVEF
 
 • If while monitoring monthly, LVEF remains <40%: reconsider neratinib only if appropriate and after cardiology consult. • If while monitoring monthly, LVEF increases to $\geq 40\%$: continue neratinib, monitor LVEF every 12 weeks and consider cardiac support with input from cardiologist 
B) If LVEF is between 40% to 50%: continue neratinib with caution and surveillance.
 
Initiate monthly monitoring of LVEF.
 
 • If while monitoring, LVEF falls to <40%: Follow bullet point A instructions described above. • If while monitoring, LVEF remains $\geq 40\%$: continue neratinib, monitor LVEF every 12 weeks and consider cardiac support with input from cardiology.
Symptomatic cardiac failure	
 • Neratinib should be discontinued.

Abbreviations: LVEF: left ventricular ejection fraction.

If a patient has a second episode of asymptomatic decline in LVEF that meets either of the above criteria, permanently discontinue **neratinib**, repeat LVEF in 3-4 weeks and consider cardiology consult.

Note that, for AEs other than symptomatic LVEF decline, if **neratinib** is held for >28 days, the patient should be withdrawn from the active treatment phase of the study (see [Section 10.1](#)). In case of asymptomatic LVEF decline, patients may resume **neratinib** within 1 week after LVEF recovery is documented as above, even if the timeframe exceeds 3 weeks. If a site does not provide normal ranges for ECHO or MUGA, a lower limit of normal of 50% should be used.

Hematologic Toxicity

Patients with baseline neutrophil counts of $<1.5 \times 10^9/L$ and/or thrombocyte counts of $<100 \times 10^9/L$ should not be treated with **capecitabine**. If unscheduled laboratory assessments

during a treatment cycle show Grade 3 or 4 hematologic toxicity, treatment with **capecitabine** should be held.

Guidelines for dose adjustments of capecitabine for hematologic toxicity due to combination of neratinib plus capecitabine are shown in **Table A2.6**.

Table A2.6: Hematologic Abnormalities Requiring Dose Adjustment of Capecitabine (When Administered in Combination with Neratinib)

NCI CTCAE v 4.0	Action
Grade 3 Neutrophil: <1000-500/mm ³ ; <1-0.5 x 10 ⁹ /L Platelet: <50,000-25,000/mm ³ ; <50-25 x 10 ⁹ /L Hemoglobin decreased: <8 g/dL; <4.9 mmol/L; <80 g/L; transfusion indicated	
 • Neratinib should be continued at the same dose • Hold capecitabine until event resolves or decreases to Grade 1 or Grade 2 • Reduce next capecitabine dose to 1100 mg/m² (550 mg/m² BID) • If the event recurs a 2nd time, hold capecitabine until event resolves or decreases to Grade 1 or Grade 2 • Reduce next capecitabine dose of 750 mg/m² (375 mg/m² BID) • If the event recurs/persists, discontinue capecitabine permanently.
Grade 4 Neutrophil: <500/mm ³ ; <0.5 x 10 ⁹ /L Platelet: <25,000/mm ³ ; <25 x 10 ⁹ /L Hemoglobin decreased: life-threatening consequences; urgent intervention indicated	
 • Neratinib should be continued at the same dose. • Capecitabine should be discontinued permanently OR if the Investigator deems it to be in the patient's best interest to continue, hold capecitabine until resolved to Grade ≤ 1 • If the Investigator decides to resume capecitabine, reduce the dose to 750 mg/m² (375 mg/m² BID) • If the event recurs/persists, discontinue capecitabine permanently

Abbreviations: BID: twice daily; L=liter; NCI CTCAE v 4.0: National Cancer Institute Common Terminology Criteria for Adverse Events Version 4.0.

Hand and Foot Syndrome

Guidelines for dose adjustments of neratinib and capecitabine for toxicity of Hand and Foot Syndrome (Palmar-Plantar Erythrodysesthesia syndrome) due to combination of neratinib plus capecitabine are show in **Table A2.7**.

Table A2.7: Hand and Foot Syndrome (Palmar-Plantar Erythrodysesthesia Syndrome) Requiring Dose Adjustment of Neratinib and Capecitabine

NCI CTCAE v4.0	Action
Grade 1: Minimal skin changes or dermatitis (e.g., erythema, edema, or hyperkeratosis) without pain	
 • Continue neratinib and capecitabine at starting dose

NCI CTCAE v4.0	Action
Grade 2: Skin changes, e.g., peeling, blisters, edema, or hyperkeratosis, with pain, limiting instrumental ADL. PI: painful erythema and swelling of the hands and/or feet and/or discomfort affecting ADL.	
 Continue neratinib at starting dose level and hold capecitabine until recovery or to \leqgrade 1, then resume at starting dose. If the event recurs/persists, continue neratinib at starting dose level and reduce capecitabine dose to 1100 mg/m^2 (550 mg/m^2 BID)

Table A2.7: Hand and Foot Syndrome (Palmar-Plantar Erythrodysesthesia Syndrome) Requiring Dose Adjustment of Neratinib and Capecitabine (Continued)

NCI CTCAE v4.0	Action
Grade 3: Severe skin changes, e.g., peeling, blisters, edema, or hyperkeratosis, with pain, limiting self-care ADL. PI: moist desquamation, ulceration, blistering or severe pain of the hands and/or feet and/or severe discomfort limiting self-care ADL	
 Continue neratinib at starting dose level and hold capecitabine until recovery or to grade ≤ 1, then reduce dose to 1100 mg/m^2 (550 mg/m^2 BID) If the event recurs/persists, continue neratinib at starting dose level and capecitabine dose of 750 mg/m^2 (375 mg/m^2 BID)

Abbreviations: ADL: activities of daily living; BID: twice daily; NCI CTCAE v 4.0 National Cancer Institute Common Terminology Criteria for Adverse Events Version 4.0.

Pancreatitis

Guidelines for dose adjustments of neratinib and capecitabine for pancreatitis due to combination of neratinib plus capecitabine are show in [Table A2.8](#).

Table A2.8: Recommendations for Dose Adjustment of Neratinib and Capecitabine and Management of Patients with Pancreatitis

NCI CTCAE v.4.0	Action
Grade 2 Pancreatitis: Enzyme elevation or radiologic findings OR Grade 3 Pancreatitis: Severe pain; vomiting; medical intervention indicated (e.g., analgesia, nutritional support)	
 Temporarily suspend (i.e., hold) neratinib and capecitabine Evaluate for any possible alternative causes If no alternative cause for pancreatitis is identified, discontinue neratinib and capecitabine permanently. If an alternative cause is identified (e.g., gallstones) or enzyme levels return to baseline within 3 weeks with clinical recovery, re-start treatment with reduced doses of neratinib 160 mg and capecitabine 1100 mg/m^2 (550 mg/m^2 BID). If the event occurs a second time, discontinue neratinib and capecitabine permanently.
Grade 4 Pancreatitis: Life-threatening consequences; urgent intervention indicated	
 Discontinue neratinib and capecitabine permanently.

Abbreviations: BID: twice daily; NCI CTCAE v 4.0 National Cancer Institute Common Terminology Criteria for Adverse Events Version 4.0

